11.4 Rescreening

At the discretion of the investigator, a patient who previously failed screening may be rescreened. All screening tests, including those conducted prior to rescreening, must still occur within the validity windows.

11.5 Informed Consent

IMPORTANT: The Code of Federal Regulations requires that the consent form signed by the Patient must be dated at the time consent is given. Also, medical records must contain documentation that informed consent was obtained prior to participation in a study. (21 CFR Parts 50 and 812)

The Investigator may determine whether potential Patients are interested in participating in an investigation, but shall not request the written informed consent of any Patient to participate, and shall not allow any Patient to participate before obtaining Institutional Review Board (IRB) approval and prior to receiving documentation of FDA approval from the Sponsor. The consent process shall begin before care is altered beyond the scope of a routine comprehensive examination for the purpose of participating in this study.

All Patients in this research study should be completely informed about the purpose, duration, and pertinent details of the study. If the informed consent is amended by the Sponsor during the study, the investigator is responsible for ensuring the IRB reviews and approves the amended form. The informed consent must be obtained using a written form that has been approved by the IRB and includes all *Basic Elements of Informed Consent* and pertinent *Additional Elements* (21 CFR Part 50.25). The informed consent discussion and process with the potential study subject shall be documented in progress/clinic notes or other source documentation. In the event a potential participant is unable to be seen in person, alternative methods of consenting (via telemedicine, including, but not limited to phone call, video or virtual office/remote visit, electronic signature or any combination of these methods) is allowed provided the consenting process is thoroughly documented in the study records and the signed consent form is maintained in the study records.

The Investigator must keep the original signed copies of all consent forms in the Patient's medical records and provide a copy to each Patient. If new information becomes available during the course of the study, the information will be provided to new and existing patients, and if relevant, request existing patients to confirm their continued participation in the study by signing an amended informed consent or consent addendum.

11.6 Patient Privacy

The investigator agrees to comply with all applicable federal, state, and local laws and regulations relating to the privacy of patients' health information, including, but not limited to, the Standards for Individually Identifiable Health Information, 45CFR Parts 160 and 164 and in accordance with the Health Insurance Portability and Accountability Act of 1996 (HIPAA), which states all patients should be informed of potential uses and disclosures of their medical information for research purposes, and their rights to access information about them by covered entities. Each Investigator will follow the procedures for securing HIPAA compliance as directed by their respective IRB or Privacy Board, and to obtain written authorization to use and disclose patient information for all clinical research and research involving questioning of the patient's or patients' physician(s). Per individual site procedures, this authorization may be included as part of the patient informed consent form.

Page 29 of 65

11.7 Strategies for Recruitment and Retention

Patients will be recruited through a variety of media. Patients may be actively recruited through IRBapproved web-based advertising, television, radio, and newspaper ads. Patients will be financially compensated for their study participation. The amount of compensation and schedule of payments will be documented in the ICF.

11.7.1 Special Population

This study will not focus on any particular subset of patients based on ethnicity or race. Further, no patient will be excluded from the study on the basis of racial or ethnic origin. The racial and ethnic composition of the study is expected to represent the demographics of the typical population seeking relief menorrhagia in the geographical area around the investigational sites. The age of the patients will typically be in the 30 - 50 year old range, the most common ages for menorrhagia.

No patients from the vulnerable population shall be enrolled in the trial. Specifically, elderly patients will not be included because these women are likely post-menopausal; and pediatric patients will not be included in this study because they do not meet the minimum age criteria and because it would be improper to have them undergo a procedure that would limit their potential fertility on a permanent basis.

11.7.2 Control of Bias Section

Upon receipt of IRB/ethics approval, patients with menorrhagia will be considered for the study until the site reaches its enrollment goal. Careful documentation will be kept tracking potential patients' eligibility and consent acceptance or rejection. To maintain a balanced population in the study, no single investigational site will be permitted to enroll more than 35% of the entire study population.

Non-response bias will be prevented by offering reasonable expense reimbursement and incentives to participate in the study. Every effort should be made to send appointment reminders to facilitate completion of study visits within study windows.

11.8 Patient Discontinuation and Replacement

Patients are free to terminate their participation (with or without reason) in the study at any time. Likewise, a patient may be terminated from the study by the investigator or the Sponsor, MicroCube, at any time if either investigator or Sponsor determines that it is not in the patient's best interest to continue participation. Enrolled patients that are terminated because of lack of compliance to protocol will not be replaced and will be considered lost to follow-up. If a patient is terminated prior to the 12-month follow up visit, this patient will be considered a treatment failure.

11.8.1 Reasons for Termination

Every patient should remain in the study until completion of the 36-month follow-up period. Whenever possible, an exit visit should be conducted to record reason(s) for withdrawal, retrieve study materials (PBLAC diaries) and complete relevant visit assessments such: AEs, concomitant medications, patient's menstrual status, NRS for dysmenorrhea-related pain and MIQ. Conceivable reasons for early patient discontinuation may include, but are not limited to, the following:

• Patient Withdrawal (voluntarily terminates consent): Patient participation in this clinical study is voluntary. The patient may choose to discontinue participation (refuse all subsequent testing) at any time without loss of benefits or penalty.

- **Discontinuation:** Patient participation may be discontinued by the patient or investigator because of a treatment modality change, organ transplant, transfer, death or prolonged hospitalization. The Sponsor may also decide to discontinue the testing of the study device.
- **Investigator-initiated Termination:** The Investigator may terminate the patient's participation without regard to the patient's consent if the Investigator believes it is medically necessary. In addition, the following circumstances may require early termination:
 - Patient is unable or unwilling to cooperate with study staff;
 - Emergence of clinically relevant serious adverse events, laboratory abnormalities or other medical condition or situation occurs such that continued participation would not be in the best interest of the patient;
 - Pregnancy
 - o Death
- Exclusion Criterion Discovered After Enrollment: A small number of patients may be enrolled despite meeting an exclusion criterion. This will be documented by the study personnel on the eCRF and will be considered a protocol deviation (PD), not termination.
- Lost-to-Follow-up: This category accounts for patients whose status is unclear because they fail to appear for study assessments/visits without stating intention to terminate consent. The data from this patient is still eligible for the intent-to-treat dataset. Site personnel should make all reasonable efforts to locate and communicate with the patient, at each contact time point, including:

A minimum of three (3) telephone calls to contact the patient should be attempted. Each attempt should be recorded in the patient's medical record, including date, time, and initials of site personnel attempting the contact.

If telephone calls are unsuccessful, a certified letter (with mailing receipt and electronic confirmation of delivery) should be sent to the patient.

If the above-mentioned attempts at communicating with the patient are unsuccessful, the patient will be considered lost-to-follow-up.

NOTE: If the patient is contacted, the patient is no longer considered lost-to-follow-up and study visits will resume at the next applicable time point.

In all cases, the reason(s) for withdrawal, if given, must be recorded on the appropriate eCRF and in the patient's medical record. If more than one reason is cited for withdrawal, study personnel must identify the most significant reason and record this reason on the eCRF. Investigators must also report all patient withdrawals to their IRB as defined by their institutions' procedures. Patients who withdraw or are withdrawn from the study or are lost to follow-up will not be replaced.

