9.3 Secondary Outcome Measures

Secondary effectiveness and safety outcome measures will be assessed at the timepoints described below.

The secondary safety outcome measure at 24 and 36 months will include all device or procedure-related adverse device effects, SAEs and unanticipated adverse device effects (UADE) are defined in **Section 14 Adverse Event Reporting**.

Any medical surgical intervention to treat abnormal bleeding following the ablation procedure is considered a treatment failure. If menstrual status is assessed as "High/Heavy" by the investigator at the 24 or 36-month follow-up, the patient will be considered a treatment failure.

Secondary effectiveness outcome measures will include the following:

Patient Global Evaluation (PGE): at 6, 12, 24 and 36 months

- Patient satisfaction with treatment
- Menstrual status
- Recommend to friends

Investigator Global Evaluation (IGE): at 6, 12, 24 and 36 months

- Investigator satisfaction with treatment
- Menstrual status

Quality of Life Measures: at 6, 12, 24 and 36 months

- Improvement of quality of life as measured by:
 - Menorrhagia Impact Questionnaire (MIQ)
 - o Dysmenorrhea-related Numerical Rating Scale (NRS) pain score

Procedure:

•

- Endometrial ablation procedure-related Numerical Rating Scale (NRS) pain score
 - The following parameters will also be collected:
 - Total procedure time
 - Total treatment time (total energy delivery time)

Page 24 of 65

CONFIDENTIAL & PROPRIETARY

- Total procedure energy in joules
- Anesthesia regimen
- Procedure-related pain at pre-procedure (baseline), discharge and 24-hours postprocedure
- Need for cervical dilation

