12.9 Durability Visits Conducted 24 and 36 Months (± 8 weeks) After Treatment

The 24 and 36-month visit may be conducted via phone, letter, email or in person as described in Section 12.1.

The 36-month visit is the final study visit. Complete both the 36-Month Visit and the Study Completion eCRFs.

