14.1.2 Serious Adverse Events (SAEs)

A serious adverse event is any untoward medical occurrence that results in one of the following:

- Led to death
- Led to serious deterioration in the health of the subject, that either resulted in
 - A life-threatening illness or injury, or
 - o A permanent impairment of a body structure or a body function, or
 - o In-patient hospitalization or prolongation, or
 - Medical or surgical intervention to prevent life-threatening illness or injury or permanent impairment to a body structure or a body function,
- Led to fetal distress, fetal death, congenital abnormality or birth defect
- Note: Planned hospitalization for a pre-existing condition or a procedure required by the protocol, without serious deterioration in health, is not considered a serious adverse event.

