14.1.3 Anticipated Adverse Device Effects Associated with Endometrial Ablation

With all endometrial ablation procedures, serious injury or death can occur. The following adverse effects could occur or have been reported in other EA studies and may occur when the Minitouch System is used. The listing includes potential risks/effects associated with administration of anesthesia.

Table 14-1: Anticipated Adverse Device Effects of Endometrial Ablation

More Commonly Reported Device/Procedural and/or Post-Procedural Complications (occurs in 20 or more patients out of 100)

- Cramping or pelvic pain
- Nausea and vomiting
- Vaginal bleeding or spotting
- Vaginal discharge and/or unpleasant vaginal smell or burning or other abnormal sensation

Other Common Possible Adverse Device Effects (occurs in 20 or less patients out of 100)

- Abdominal pain or bloating
- Adhesions
- Backache
- Cervical stenosis
- Chills
- Constipation
- Diarrhea
- Fever
- Headache
- Hematometra (collection of blood in the uterus)
- Lightheadedness or fainting
- Menometrorrhagia (abnormally heavy, prolonged and irregular uterine bleeding)
- Post-ablation tubal sterilization syndrome (PATSS)
- Skin rash and/or itching burning sensation
- Weakness, fatigue, sleepiness, lack of concentration, dizziness

Rare Adverse Device Effects (occurs in 5 or less patients out of 100)

- Agitation
- Air embolism (blood vessel blockage caused by an air bubble)
- Cardiac complications
- Cervical or vaginal laceration or tear
- Complications leading to serious injury or death
- Difficulty with defecation or micturition
- Dyspareunia (painful intercourse)
- Dysuria (painful urination)
- Endometritis or Endomyometritis (inflammation of the uterine tissue)
- Hemorrhage (excessive bleeding)
- Hydrosalpinx (blocked fallopian tubes filled with fluid)
- Infection or sepsis
- Pelvic inflammatory disease (PID)
- Pregnancy-related complications
- Tissue injury (thermal, mechanical or electrical)
- Uterine necrosis (uterine tissue death due to lack of blood supply)

Page 42 of 65

- Uterine perforation (hole in the uterus)
- Vulvar pruritis (itchiness of the vulva)

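### Section 11.8.1 lets pregnancy, a change of treatment or prolonged hospitalization end follow-up after a one-time procedure, so related events that begin afterwards can be missed

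*Combined protocol and SAP*

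**What the plan says.** Section 11.8.1 opens by expecting every woman to stay to the end of the 36-month follow-up. It then lists conceivable reasons for leaving early, and two of its bullets matter here.

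- **Investigator-initiated termination.** The list begins "In addition, the following circumstances may require early termination". Pregnancy appears with no qualifier. SAEs appear as "Emergence of clinically relevant serious adverse events, laboratory abnormalities or other medical condition or situation occurs", but only "such that continued participation would not be in the best interest of the patient".
- **Discontinuation.** "Patient participation may be discontinued by the patient or investigator because of a treatment modality change"; the same sentence goes on to name prolonged hospitalization. No best-interest condition is attached.

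The safety outcomes reach further than these exits allow:

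- Section 9.2 sets the primary safety endpoint as related SAEs at 12 months, expected in under 1%.
- Section 9.3 says: "The secondary safety outcome measure at 24 and 36 months will include all device or procedure-related adverse device effects", together with SAEs and UADEs.
- Table 14-1 lists "Pregnancy-related complications" as an anticipated device effect.
- Section 14.1.2 counts as serious an event that "Led to fetal distress, fetal death, congenital abnormality or birth defect".
- The synopsis makes intervention for abnormal bleeding at any time after ablation a secondary safety outcome. Section 7.2.2 frames the related objective over 12 months.

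Section 13.16.3 confirms that the procedure is done once.

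**The concern.** In a drug trial, a list of this kind often protects the patient by stopping treatment. Here no study treatment remains to be stopped after Day 0, so leaving the study mainly ends observation. Two of the exit grounds also lie close to the safety outcomes. A woman who conceives after ablation may leave at the pregnancy, before a pregnancy complication or fetal outcome could occur. A woman who moves to another treatment may be having the kind of bleeding intervention the trial wants to count. Hospitalization is itself one of the routes to an SAE in section 14.1.2.

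If follow-up ends for reasons linked to safety, the missing follow-up may be informative, and with a rare endpoint a single unseen event is visible in the result. The effectiveness analysis has a rule for this: section 11.8 scores termination before month 12 as failure. Sections 17.4 and 17.5 have no matching rule for incomplete safety follow-up.

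**Working it through.** **1. Does any provision collect events that start after an individual termination?**

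| Provision | What it covers | What it leaves open |
|---|---|---|
| 11.8.1, exit visit | One visit, where possible, including AEs | Anything later |
| 12.10, termination visit | AEs and SAEs if the woman leaves before month 12 | Exits after month 12; anything later |
| Table 23-1, footnote 2 | Attempt all assessments if she terminates during a visit | Anything later |
| 14.2.3 | Recorded AEs monitored until resolved or explained | Events not yet begun |
| 21.7.2 | Standard-of-care follow-up if the trial is stopped or suspended | Individual terminations |

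None does. By contrast, a woman lost to follow-up receives at least three calls and, if those fail, a certified letter, and her visits resume if she is reached (11.8.1).

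**2. Which events can be lost?**

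- *An SAE that itself triggers termination.* The woman is in the ITT cohort (17.1.1) and her event has been recorded. A per-woman ITT rate already counts her.
- *The same woman in the PP cohort.* Section 17.1.2 requires attendance at the 12-month visit and uses PP for safety at 12, 24 and 36 months. If she leaves before month 12, she and her SAE drop out of that analysis.
- *A woman who leaves for pregnancy, treatment change or another non-SAE reason.* A first related SAE after exit is unseen in both cohorts, as are pregnancy outcomes and later non-serious related events.

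**3. The plan's sample size, used here as the denominator.** Section 17.2.1 gives a null rate of 66%, an expected rate of 78%, one-sided alpha 0.025, 80% power and null variance:

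n = [1.960·√(0.66·0.34) + 0.842·√(0.78·0.22)]² / 0.12² = 113.3, rounded up to 114, as stated.

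For dropout, 114 × 1.10 = 125.4, giving the stated 126 (dividing by 0.90 gives 127). The point does not change the sample size.

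**4. Illustration of sensitivity.** The documents give no number of women expected to leave for these reasons, so the number of unseen first SAEs is an assumption and is varied. Intervals are exact (Clopper-Pearson) two-sided 95%, N = 126.

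| First related SAEs | Rate | 95% interval |
|---|---|---|
| 0 | 0% | 0 to 2.89% |
| 1 | 0.79% | 0.02 to 4.34% |
| 2 | 1.59% | 0.19 to 5.62% |
| 3 | 2.38% | 0.49 to 6.80% |
| 4 | 3.17% | 0.87 to 7.93% |

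At a true rate of 1%, the expected count is 126 × 0.01 = 1.26, and the chance of at least one event is 1 − 0.99¹²⁶ = 72%. One unseen event therefore turns 0 into 1, or doubles 1 to 2. The second case moves the rate from 0.79% to 1.59%, across the protocol's own expectation of under 1%.

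**The case against.** The case on the other side is substantial, and much of it stands.

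- *Nothing is mandatory.* The reasons are conceivable ones that may apply, and the section begins with retention to 36 months. This stands. The text permits the loss and does not require it.
- *The SAE ground is already limited.* A reader might infer that any SAE can end follow-up. The documents do not support that, because the bullet applies only where staying is not in the patient's best interest, a power section 11.8 also gives separately.
- *SAE-triggered exits do not lower the primary ITT rate.* A reader might infer informative censoring of the primary safety rate from this ground. As shown above, the triggering event is already counted.
- *Safety follow-up is not cut off altogether.* The exit and termination visits collect AEs, and recorded events are followed. This stands for events known at exit, including a bleeding intervention that is itself the reason for leaving.
- *Pregnancy should be rare.* Women must not wish to retain fertility and must use reliable contraception, and Table 14-1 puts pregnancy complications in its rare group. This limits the number of women, not the value of each outcome.
- *No success decision depends on it.* Safety has no hypothesis or performance goal in sections 17.4 and 17.5.
- *Details may sit elsewhere.* The CEC charter and a fuller SAP are separate and were not available. They might settle adjudication and analysis, but neither can recover data that the protocol does not tell sites to collect.

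What remains is narrower: the unqualified grounds, and the absence of any rule for events that begin after a woman's participation ends.

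**Conclusion.** The point holds in this limited form. Section 11.8.1 allows participation to end for pregnancy, treatment modality change or prolonged hospitalization with no best-interest condition, and this is at odds with its own retention statement and with the safety outcomes in sections 7.2.1, 9.2 and 9.3. The possible loss is pregnancy outcomes, later or new related events, and first SAEs in women who left for a non-SAE reason. In addition, women who leave before the month 12 visit are missing from the PP safety analysis.

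The size cannot be derived from the documents. The shift in the upper limit from 2.9% to 4.3% assumes one unseen first event among 126 women; it shows how sensitive a rare endpoint is and does not estimate bias. It would be wrong to conclude that the primary safety rate is known to be understated, or that the effectiveness conclusion is affected. This is a cheap improvement, not a flaw that threatens the trial.

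**What to change.** Reconcile section 11.8.1 with its retention statement and with the safety outcomes in sections 7.2.1 and 9.3:

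1. Remove pregnancy, treatment modality change and prolonged hospitalization as stand-alone reasons to end study follow-up. The investigator's and sponsor's power to terminate in the patient's best interest can stay.
2. State that, unless consent is withdrawn, these women and any woman terminated in her best interest remain in AE and SAE follow-up to month 36. Section 12.1 already accepts telemedicine visits, and section 12.9 says "The 24 and 36-month visit may be conducted via phone, letter, email or in person".
3. State that any pregnancy is followed to outcome and sent to the CEC.
4. State that effectiveness is still scored under the existing endpoint rules. The failure rule in section 11.8 is triggered by termination, so the text should say how it applies to a woman who stays only in safety follow-up.

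The change concerns data collection and leaves clinical care to the investigator. It costs protocol wording, a few extra remote contacts and possibly a slightly higher reported event rate. The sample size is unchanged.
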